Research Protocol

Title: The CIS Trial
Principal Investigator: [name]
Other Investigators: [name]
[name]
[name]
[name]

Institutional affiliations: Akron General Medical Center

I. BACKGROUND AND SIGNIFICANCE

A. Treatment for patients who suffer an ischemic stroke typically depends upon a fixed and arbitrary time window. Therapy typically includes intra-venous treatment (IVT) for patients who present within 4.5 hours of beginning of symptoms and intra-arterial treatment (IAT) for patients who arrive within 8 hours of symptomatic onset as the standard of care [1]. During IVT, tissue plasminogen activator (tPA) is injected into a vein in the arm. IAT is an endovascular procedure in which a catheter is inserted into an artery and directed to the site of the blocked blood vessel in the brain. The clot is removed using a mechanical device with or without an injection of tPA directly at the site of the clot. Several types of mechanical devices are approved for clinical use. Not all patients who arrive within this fixed time window receive IVT or IAT, since certain defined subgroups of patients do not improve despite complete revascularization (i.e. opening of the occluded blood vessel) within the accepted time window.

Patients who should not be treated include those who demonstrate large areas of hypodensity (i.e. dark tissue) on head computerized tomography (CT) scan, those with an intracranial hemorrhage, and those with other stroke mimics such as herpetic encephalitis. [2,3] To further improve the criteria for determining which patients should receive therapy, a group of investigators developed the ASPECT Score, an imaging scale based on head CT. Patients with an ASPECT Score of < 6 will generally not improve with treatment.

- B. To further improve patient selection (decrease the number of patients in whom successful revascularization is clinically futile) other noninvasive testing methods have been applied, including CT perfusion, magnetic resonance imaging (MRI) perfusion, and diffusion based images. [4-8] Despite the various forms of noninvasive testing, the good clinical outcome (GCO) rate consistently lags behind the rate of good revascularization, by at least 30-40%.

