The investigators believe that focusing only on time and static noninvasive imaging for selecting patients suitable for IAT ignores critical physiological factors, i.e. differentiating blood-deprived yet viable brain tissue from nonviable tissue. The principal investigator has developed a system referred to as the Capillary Index Score (CIS) that helps differentiate between viable and nonviable tissue. The CIS is obtained during the diagnostic cerebral angiogram (DCA) performed as a necessary step at the time of treatment. The fact that the CIS is obtained just before proceeding with treatment differentiates it from all other currently employed neuroimaging-based patient selection strategies, which are sometime done an hour or more prior to proceeding with the treatment. Tissue in the ischemic area (tissue blocked from its usual primary blood supply), but fed through secondary vessels (pial collaterals) represents tissue that can recover if the clot can be removed. This secondary blood supply is shown by a blush surrounding the capillaries on the DCA. The investigators believe that collateral blood flow graded by this system is more accurate than time to treatment in determining the patients who should be given endovascular treatment. The CIS is a 4 point simple system (0-3). The ischemic territory is divided into 3 sections. If a section exhibits a capillary blush it is given one point. If the three sections of the ischemic territory have a capillary blush the final score is 3. If none exhibit capillary blush the score is zero. Based on the 1/3 hypodensity rule we considered the CIS to be poor (pCIS) if more than 1/3 of the ischemic territory has no capillary blush (CIS=0, 1). A score of 2 or 3 is considered a favorable CIS (fCIS). DCA (injecting the ischemic territory only) is a necessary step performed prior to clot removal. Certain operators inject only the occluded vessel instead of obtaining more complete imaging which assesses the anatomical and physiological status of collateral vessels. It is currently the usual practice of many neurointerventionalists to obtain a complete set of DCA films prior to treatment which assess collateral circulation. This may increase the time of the intervention by 2-5 minutes, which most neurointerventionalists believe carries an extremely low risk and does not affect outcome.

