of good outcomes for these recent trials in the IAT arms have varied widely (52-71%). The investigators believe that a primary factor explaining differences between studies is the portion of people with favorable CIS included in the studies. Interestingly the ratio between the rate of good outcomes in the treatment arm vs. the control arm (no IAT) has been stable across the different positive trials showing the effect of IAT at approximately 1.7 for all of these recent trials, similar to the PROACT II trial more than 15 years ago. [3]. The investigators believe the stagnation of this ratio at 1.7 is evidence that the selection criteria have not improved despite improvement in the rate of revascularization. Based on the existing data, the investigators would like to evaluate the merit of CIS as a primary tool for patient selection in IAT, hoping to prove that the rate of treated to untreated improvement is on the order of 6 to 7. We expect that if we select for patients with fCIS and obtain good revascularization to obtain around 80% GCO in the treated arm. We also expect successful revascularization to be futile for patients with pCIS.

E. The principal investigator believes that the CIS for each patient is determined genetically. In order to explore the genetic link to the CIS, this trial also aims to perform SNP-trait association analysis to identify the genetic loci linked to CIS and stroke outcome in patients suffering from AIS. *Dce1* has recently been found to be responsible for approximately 85% of the variation in collateral extent and it is likely that polymorphisms of *Dce1* are a major determinant of the wide variation in collateral scores in humans. If it is shown that *Dce1* is correlated to CIS and both are predictive outcomes for EVT, then this will further increase confidence in CIS as an assessment of collateral status, strengthen patient stratification of patients to define course of treatment for best outcome and least risk, and suggest the use of genetic testing in clinical decision making.

II. STUDY OBJECTIVE(S); INCLUDING SPECIFIC AIMS AND/OR HYPOTHESES

The hypothesis, or idea being tested, is that as long as patients have a favorable CIS they can be successfully treated with IAT out to 24 hours. For patients with poor CIS, success rates will be relatively low, with no benefit provided by IAT. The long term objective is to:

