The population for the study will be patients with anterior circulation acute ischemic stroke due to blockage of the intracranial internal carotid artery or middle cerebral artery (M1) within 8 hours of onset of symptoms. Typically, IAT is only offered to patients up to 6 hours, with no treatment options directly targeting the clot available after that time. Occlusion of one of these vessels will be determined based on CT angiography, magnetic resonance angiography, or DCA. Only patients 18 or over will be considered for the study. Other inclusion criteria include a score of 8 or greater on the National Institute of Health Stroke Scale (NIHSS, see appendix). Exclusion criteria will include contra-indication for IAT found on initial CT, intracranial hemorrhage, stroke mimics (tumor, herpetic encephalitis, etc.), more than 1/3 hypodensity on non-enhanced head CT prior to intervention, ASPECT Score < 6, and pre-existing disability defined as mRS ≥ 2. Pregnant women will also be excluded.

[figure not shown]

Figure 1: Study design for Phase I

Version: 6.0 5

[figure not shown]

Figure 2: Study design for Phase II

C. Assessment of Resources

The multicenter study will be carried out at up to 6 stroke centers. Each center is expected to have approximately 1 patient per month eligible for the study. Enrollment of patients will be performed at the end of imaging at each institution. At Akron General Medical Center, consent will be obtained within the DCA imaging suite. Consent will be obtained by a person qualified by the local IRB other than the treating physician. At Akron General, consent will be acquired by one of two neurointerventional lab nurses. One of these two nurses is required to be present for treatment of each patient with acute ischemic stroke, regardless of participation in a study. These nurses are familiar with all aspects of the proposed treatment methods and typical outcomes. The nurses will perform documented training on methods for obtaining consent and maintaining confidentiality of data obtained from subjects enrolled in research projects.

D. Study Procedures

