Pre-operative condition and patients outcomes will be assessed using standardized and validated measures. The primary endpoint of a mRS score will be obtained at least 90 days following treatment and again at 1 year following treatment. NIHSS score will be obtained in the emergency room before the treatment, within 24 h of treatment, and before discharge. The person who will obtain the NIHSS will be certified to obtain it. Adequacy of revascularization will be assessed at the end of treatment by the treating physician according the modified thrombolysis in cerebral infarction (mTICI) scale (see Appendix). All of these measures are standards for care and trials of acute ischemic stroke. [8-10] All case report forms will be maintained by the primary investigator at the local site, and stored within locked cabinets. The personal identifying information on the case report forms will be deidentified and assigned a code before being transferred to Akron General Medical Center for transfer of the data to a de-identified database which will be used for analysis.

IV. DATA COLLECTION

Version: 6.0

A. How and what data will be collected

Data related to patient demographics, stroke risk factors, condition prior to treatment, time of treatment, and outcomes will be collected for each patient. Data on demographics will include sex, age, and race. Data on stroke risk factors will include history of hypertension, blood pressure, prior heart attack, arrhythmias, diabetes, glucose (sugar) level at admission, and obesity. Data on condition prior to treatment will include NIHSS score determined in the emergency room. Data on time of treatment will include time from symptoms to arrival at emergency room, time to start of DCA, and time to end of the procedure. Data on outcomes will include mRS at 3 months, mRS at 1 year, NIHSS score within 24 hours and at discharge, and complications brain edema and intra-cranial hemorrhage. Other parameters within these categories could be acquired as deemed necessary for analysis of the data.

V. DATA ANALYSIS

A. Sample Size Considerations

Phase I

A power analysis has been performed based on the previous retrospective analyses of the relationship between outcomes and the CIS for phase I. The sample size was calculated for the influence of the combination of CIS and revascularization on good outcomes (mRS \leq 2) based on the following assumptions.

- The percentage of patients with fCIS will be 60%

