 ADAM17, CNX37 and their related gene pathways.
- Subgroup analysis will be performed for ethnicities.
- Taqman assays and/or exome sequencing of significantly associated SNPs and/or genes.
- Pending results, a future validation study will follow this discovery study by increasing the sample size.

B. Statistical Methodology

Data for the proposed study will be analyzed using comparison of proportions and multivariable logistic regression. Analysis of proportions based on Fisher exact tests will be used to compare rates of good outcomes between the fCIS and pCIS groups as the primary end point for phase I. The influence of successful revascularization on outcomes for patients with fCIS or pCIS will also be analyzed using Fisher exact tests as the secondary end point.

Binary and/or ordinal multiple logistic regression analyses will be used to evaluate the influence of multiple parameters on the likelihood of a good outcome. These parameters will include CIS, mTICI score, NIHSS score, time to revascularization, age, sex, history of diabetes mellitus, history of high blood pressure, history of coronary artery disease. The same analyses will be performed for phase II, instead focusing on the treatment groups rather than the CIS classification.

VI. DATA AND SAFETY MONITORING PLAN

A. Describe any provisions for monitoring the data for safety

A safety committee will monitor the data. The safety committee will be composed of at least 3 voting members. At least two members will be neurologists, neuroradiologists or neurointerventionalists with experience treating acute ischemic stroke who are not investigators at any of the sites. These members will not be affiliated with the institution of the principal investigator, any sub- investigator, or Akron General Medical Center. At least one member with a background in biostatistics who is not an investigator or affiliated with Akron General Medical Center will also be on the committee.

For phase I, the only deviations in normal standards of care are:

Version: 6.0

- 1- the extra few minutes for full DCA for some centers as opposed to injecting only the occluded vessel
- 2- Adding IAT to treatment of patients seen between 6 and 24 hours of onset of symptoms.

The safety committee will be looking at known potential complications for IAT in both fCIS and pCIS groups. These include:

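### ASPECTS is scored for eligibility but neither named for collection nor modelled, so the plan cannot show whether CIS predicts good outcome independently of ASPECTS grade among CT-eligible patients

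*Combined protocol and SAP*

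**What the plan says.** **Role of CT in the rationale.** Section I.A presents ASPECTS as the existing CT-based selection score: "Patients with an ASPECT Score of < 6 will generally not improve with treatment". Section I.C argues that "focusing only on time and static noninvasive imaging for selecting patients suitable for IAT ignores critical physiological factors" and offers CIS as the answer. Section I.D states the aim as to "evaluate the merit of CIS as a primary tool for patient selection in IAT".

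**Eligibility.** Section III.B excludes "more than 1/3 hypodensity on non-enhanced head CT prior to intervention" and also "ASPECT Score < 6, and pre-existing disability defined as mRS ≥ 2". Every enrolled patient must therefore have been assessed against the ASPECTS threshold.

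**Data collection.** Under section IV.A, "Data on condition prior to treatment will include NIHSS score determined in the emergency room". No imaging score is named there. The paragraph ends with a clause that allows further parameters within the listed categories if the analysis needs them.

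**Analysis.** The Phase I primary analysis in section V.B is a Fisher exact test of good outcome in fCIS v pCIS, without adjustment. The logistic regression follows: "These parameters will include CIS, mTICI score, NIHSS score, time to revascularization, age, sex", and then histories of diabetes, high blood pressure and coronary artery disease. That makes nine terms, none of them a baseline imaging score.

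**The concern.** Section I.C criticises two existing selectors, time and static imaging. Time is both collected (IV.A) and modelled (V.B). The CT score is neither, although screening requires it.

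Among enrolled patients ASPECTS can still run from 6 upward (to 10, taking that as the top of the scale, which the protocol does not state). If patients with poor capillary blush also tend to sit lower in that range, and lower scores go with worse outcome, part of the raw fCIS-pCIS difference belongs to a CT score that was available before the angiogram. A reader deciding whether an angiographic score tells more than the CT grade would get no answer from the planned analyses. This is separate from adjustment for age and stroke severity, which the regression already covers.

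**Working it through.** **1. The plan's own figures (section V.A).** The inputs are 60% fCIS, 50% good revascularization, and good-outcome rates of 70% and 20% in fCIS and 20% and 10% in pCIS (good and poor revascularization respectively).

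- fCIS: 0.5 × 0.70 + 0.5 × 0.20 = 0.45
- pCIS: 0.5 × 0.20 + 0.5 × 0.10 = 0.15
- Planned difference: 30 points
- Overall: 0.6 × 0.45 + 0.4 × 0.15 = 0.33, so 60 × 0.33 = 19.8 good outcomes among 60 completers

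The stated sample size of 54 reproduces. fCIS with good revascularization (30% of patients, rate 0.70) is compared with all others, whose rate is (0.3 × 0.2 + 0.2 × 0.2 + 0.2 × 0.1)/0.7 = 0.171. With two-sided alpha 0.025, power 0.90, allocation ratio 0.7/0.3 and a continuity correction, the normal-approximation formula gives 16 + 38 = 54. Other formulas also land on or near 54, so the one used cannot be identified. None of these inputs involves ASPECTS.

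**2. How large a raw difference could arise with no CIS effect beyond ASPECTS?** The documents give no joint distribution of CIS and ASPECTS, so these inputs are assumed:

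- ASPECTS 8-10 in 70-80% of fCIS and 30-40% of pCIS patients
- Good outcome in 45-50% at ASPECTS 8-10 and 15-20% at 6-7, the same in both CIS groups

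Group rate = share × high rate + (1 − share) × low rate. Rejection is the exact probability for a two-sided Fisher test at 0.05 with 36 v 24 patients (60 completers, 60% fCIS). The plan does not state sidedness.

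| Shares with ASPECTS 8-10 (fCIS, pCIS) | Rates (8-10, 6-7) | fCIS v pCIS | Difference | Rejection |
|---|---|---|---|---|
| 70%, 40% | 45%, 20% | 0.375 v 0.300 | 7.5 points | 6.4% |
| 70%, 30% | 45%, 15% | 0.360 v 0.240 | 12 points | 12.0% |
| 80%, 30% | 50%, 15% | 0.430 v 0.255 | 17.5 points | 22.6% |

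The first and last rows are the extremes over all 16 combinations. When the two groups share one rate, the same test rejects in at most 3.5% of trials. As shares of the planned 30 points, the differences are 7.5/30 = 25% and 17.5/30 = 58%.

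These rejections are not errors about the raw association, which is real in the illustration. They mislead only if read as evidence that CIS adds to ASPECTS grade.

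**3. A second illustration with a different model.** This is a simulation at 60 patients with ASPECTS uniform on 6-10 and a log-odds for ASPECTS of 0.5 to 1.0 per standard deviation (again assumed). With no CIS effect, the unadjusted CIS test rejects in about 5-6% at correlation 0 between ASPECTS and latent CIS, 9-20% at 0.5 and 12-35% at 0.7. Adjusting for ASPECTS holds rejection at about 6%. With a true CIS odds ratio of 4.6 ((0.45/0.55)/(0.15/0.85)) and an ASPECTS log-odds of 0.5, the adjusted test has about 69% power at correlation 0 and 51% at 0.7.

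**4. What the data can support.** Events per term are 19.8/9 = 2.2 for the planned regression, 19.8/10 = 2.0 with ASPECTS as a tenth term, 19.8/4 = 5.0 for CIS, ASPECTS, age and NIHSS, and 19.8/2 = 9.9 for CIS and ASPECTS alone.

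**The case against.** A reader might infer that the trial cannot show CIS adds anything to CT selection. The documents do not support that. Everyone enrolled has an ASPECT score of at least 6 and no more than 1/3 hypodensity, and section I.A uses ASPECTS as a cut-off. A difference between fCIS and pCIS inside that population is evidence that CIS separates patients whom the CT rule accepts. This stands, and it limits the point to ASPECTS grade above the cut-off.

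A reader might also infer that ASPECTS will be unavailable. That does not follow either. The closing clause of IV.A would permit recording it, and IV.A also omits CIS and mTICI, which V.B analyses, so the list is not complete. But the clause permits and does not commit. Eligibility needs only whether the score is below 6, so the value itself may not reach the central database. And CIS and mTICI are named in the analysis, while ASPECTS is named in neither place.

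Nor do the documents show that CIS merely restates the CT score. Section I.C takes the CIS cut from the 1/3 hypodensity rule, but that sets a threshold and does not establish correlation among CT-eligible patients. The overlap in the working is assumed.

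Finally, the only explicit accuracy comparator for CIS is time to treatment (I.C), and gain in discrimination over ASPECTS is not a stated objective (II). That is correct. It makes the adjusted analysis supportive. It does not make it superfluous, given the case that section I builds against static imaging.

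**Conclusion.** The point holds in a limited form. Followed as written, the plan leaves CIS unseparated from ASPECTS grade among CT-eligible patients. A raw fCIS-pCIS difference would show separation beyond the ASPECTS cut-off and nothing about independence from the grade.

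The textual finding (needed at screening, not named for collection, not in the model) needs no assumption. The size does. Under the stated grid, ASPECTS alone could produce a quarter to somewhat over a half of the planned difference. If CIS and ASPECTS are unrelated among enrolled patients, it would produce none. The omission does not invalidate the primary test, but it is worth correcting because the value is already determined at screening.

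**What to change.** 1. Add the baseline ASPECTS value, not only whether the threshold was met, to the section IV.A data list.
2. In section V.B, prespecify a small supportive logistic model, separate from the nine-term regression: CIS plus ASPECTS as one linear term, optionally with age and baseline NIHSS, penalized if needed. Report the CIS odds ratio with its confidence interval.
3. Keep the Fisher test as primary. Do not make the adjusted test or a change in discrimination the headline result, because both would be too imprecise.
4. State in advance that a null adjusted result does not show that CIS has no added value.

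The cost is one data field and one degree of freedom. The downside is precision: with about five events per term in the four-term version, the CIS interval will be wide, and wider still if CIS and ASPECTS are strongly correlated. If the value is not recorded prospectively, recovering it may mean re-reading scans at up to six centers.

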- C. Despite applying the above selection criteria (time from onset of symptoms and findings on CT scan), the percentage of GCO has been consistently lacking behind the recanalization rates which has been steadily improving to up to 80-90%. It is clear that a significant proportion of good revascularizations are futile due to lack of clinical improvement [5-8, 9-12]

Version: 6.0

2

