- The percentage of patients with good revascularization will be 50%
- The rate of good outcomes for the combination of fCIS and good revascularization is assumed to be 70%
- The rate of good outcomes for the combination of fCIS and poor revascularization is assumed to be 20%
- The rate of good outcomes for the combination of pCIS and good revascularization is assumed to be 20%
- The rate of good outcomes for the combination of pCIS and poor revascularization is assumed to be 10%

The assumptions provide the following power analysis:

- $\alpha = 0.05$ for overall analysis and set to 0.025 for subgroup analysis comparing fCIS and good revascularization to all other groups due to multiple comparisons
- power = 0.90
- Needed Sample size = 54 patients
- An additional 6 patients completing the trial are budgeted due to risk of errors in estimated outcomes. An additional 15-20 patients are expected to be enrolled due to patients lost to the 90 day follow up and/or deviations from the protocol.

Phase II

Phase II will be an exploratory study evaluating the rates for good outcomes for patients with pCIS treated with IVT plus IAT vs. IVT (or other standard of care) only. The rate of good outcomes is expected to be approximately 13% for the IAT group with revascularization. The investigators have no prior data on expected rates of good outcomes for patients with pCIS treated with IVT only. The best possible outcome rate would be on

Version: 6.0

the order of 25% noted previously for untreated acute ischemic stroke. Due to the low levels of good outcomes, the investigators acknowledge the study will be underpowered to detect a difference between the two treatment groups for a total sample size of 30. Phase II will serve as a pilot study to initially establish estimates of rates of good outcomes for pCIS patients treated with IVT only for design of a larger prospective study.

Genetic Analysis

Genetic analysis will be performed based on the following:

- Genetic and expression analysis for the two groups based on their collateral score
- Adjust groups for cardiovascular/stroke risk factor presence and other known confounding conditions
- High density SNP array analysis will be performed for common and rare alleles
 against known collateral-related genes that have been identified in mice. These
 include human RABEP2 and its isoform RABEP1 and related gene pathways;
 VEGFA, FLK1 and their related gene pathways; NOTCH, DLL4, ADAM10,

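### The stated 90% power belongs to a contrast that is not a named endpoint; power for the primary and secondary tests depends heavily on an unexplained 50% revascularization rate and is not given

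*Combined protocol and SAP*

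**What the plan says.** Section V.A (Phase I) lists the sizing inputs. Among them are "The percentage of patients with fCIS will be 60" per cent, "The percentage of patients with good revascularization will be 50" per cent, and "The rate of good outcomes for the combination of fCIS and good revascularization is assumed to be 70" per cent. The other three cell rates are 20% (fCIS, poor revascularization), 20% (pCIS, good) and 10% (pCIS, poor). The inputs are attributed in general terms to earlier retrospective analyses. Alpha is 0.05 overall and 0.025 for fCIS plus good revascularization against all other groups. Power is 0.90 and the required N is 54, raised to 60 completers.

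Section V.B makes the Fisher comparison of fCIS with pCIS the primary endpoint. For the secondary endpoint it says: "The influence of successful revascularization on outcomes for patients with fCIS or pCIS will also be analyzed using Fisher exact tests". No power is given for either.

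The background (I.C) refers to "recanalization rates which has been steadily improving to up to 80-90" per cent. Section III.D has the treating physician grade revascularization on mTICI, and the appendix lists the grades. No section says which grades count as good.

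On pCIS outcomes, III.A expects about 15% good outcomes in Phase I. VIII.B places Phase II after a rate under 15% has been established. VI.A makes better-than-expected pCIS outcomes the main reason not to launch Phase II.

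**The concern.** Revascularization rate enters the Phase I design in three ways. It sets the all-treated good-outcome rates in fCIS and pCIS, and so the size of the primary contrast. It sets how many patients fall in the poor-revascularization cells, and so whether the secondary tests can show anything. It also sets the pCIS rate that the safety committee will take as expected when it advises on Phase II.

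An input with that much influence is given as a single unexplained value that sits poorly with the protocol's own background. The one power figure in the plan is attached to a contrast that V.B does not name as an endpoint. A reader who takes 0.90 as the power of the primary or secondary analysis would be misled, and the direction of the error depends on the revascularization rate actually reached.

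**Working it through.** **Inputs.** From V.A: 60% fCIS, good-outcome rates 70/20/20/10%, revascularization rate r = 50%. From III.A: 60 completers. Assumptions: two-sided tests (sidedness is not stated), the same r in both CIS groups, unchanged cell rates, alpha 0.05 for the V.B tests. I also use r = 80% and 90%, the range in I.C.

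**1. Reproducing N = 54.** At r = 50%, fCIS plus good revascularization is 0.6 × 0.5 = 30% of patients. The good-outcome rate in everyone else is (0.3 × 0.2 + 0.2 × 0.2 + 0.2 × 0.1)/0.7 = 17.1%. For 70% v 17.1%, two-sided alpha 0.025, 90% power and allocation k = 7/3:

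n1 = [z(α/2)·√(p̄(1−p̄)(1+1/k)) + z(β)·√(p1(1−p1) + p2(1−p2)/k)]² / (p1−p2)²

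With p̄ = 0.33, z = 2.241 and 1.282, this is (1.260 + 0.667)²/0.5286² = 13.3. The continuity correction raises it to 15.9, so 16 v 38, total 54: an exact match. (A four-group chi-square at alpha 0.05 gives 53. That is also a test of the CIS-by-revascularization combination, not the V.B primary.)

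**2. Does that figure survive a different r?** The same formula needs N = 50 at r = 80% and 52 at 90%. Exact Fisher power at N = 54, alpha 0.025, is 93% at 50% (16 v 38), 94% at 80% (26 v 28) and 93% at 90% (29 v 25). It does.

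**3. Expected rates as r varies.**
- fCIS = 0.7r + 0.2(1−r)
- pCIS = 0.2r + 0.1(1−r)
- overall = 0.6 × fCIS + 0.4 × pCIS

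**4. Exact two-sided Fisher power for the V.B tests**, 60 completers (36 fCIS, 24 pCIS):

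| | r = 50% | r = 80% | r = 90% |
|---|---|---|---|
| fCIS, all treated | 45% | 60% | 65% |
| pCIS, all treated | 15% | 18% | 19% |
| Overall | 33% | 43% | 47% |
| Primary, fCIS v pCIS | 65% | 90% | 94% |
| Within fCIS, good v poor (n) | 18 v 18 | 29 v 7 | 32 v 4 |
| Within fCIS, power | 83% | 63% | 43% |
| Within pCIS, good v poor (n) | 12 v 12 | 19 v 5 | 22 v 2 |
| Within pCIS, power | 2% | <1% | <1% |

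At r = 50% the primary contrast (45% v 15%) would need about 100 patients for 90% power by the normal approximation, or 114 with continuity correction.

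**The case against.** The plan's arithmetic is right: 54 follows from its inputs, and that contrast is powered as claimed at any r from 50% to 90%. The 50% figure is the cautious choice for the primary test, whose power rises with r. The retrospective analyses behind the inputs are not available here and may support 50%. At 50% the implied pCIS rate equals the 15% expected in III.A. V.B also puts mTICI score into the logistic regressions, so the secondary question does not rest on the Fisher tests alone. All of this stands.

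Three stronger readings are tempting, and the documents do not support them.

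- *A stated secondary power is overstated.* None is stated. Only the power implied by the inputs falls, and only within fCIS. Within pCIS the test is uninformative even at 50%, so that weakness does not come from this assumption.
- *The background implies 80% or more.* I.C gives a ceiling, and for recanalization, which need not equal good revascularization when no mTICI cut is set. One might take I.B, "the good clinical outcome (GCO) rate consistently lags behind the rate of good revascularization, by at least 30-40" per cent, and add 30 to the lower end of I.D, "of good outcomes for these recent trials in the IAT arms have varied widely (52-71" per cent, to get 82%. The same sum at the upper end is 71 + 30 = 101%, so the gap cannot apply to every trial in that range. If the lag is read as relative, V.A's own inputs give (50 − 33)/50 = 34%, inside 30-40%.
- *A higher r would bring the plan into line with 52-71% good outcomes.* Even r = 100% gives 0.6 × 0.7 + 0.4 × 0.2 = 50% with the plan's cell rates, so r alone cannot close that difference.

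**Conclusion.** The point holds as one about unstated power and an unjustified input, not as an arithmetic error. The stated 0.90 is sound for the contrast it was computed on and does not describe either V.B endpoint. At the plan's own inputs the primary test has about 65% power with 60 completers. If revascularization reaches 80-90%, the primary gains about 25 to 30 points while the within-fCIS secondary test loses about 20 to 40. No value in this range gives both tests 90% power, and none makes the within-pCIS test informative.

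The implied pCIS rate also matters for Phase II. It is 15% at r = 50%, at the VIII.B threshold and not below it, and 18-19% at 80-90%. Part of this comes from the 20% cell rate: I.D reports a maximum of 13% in pCIS with good revascularization, and using 13% would give 0.8 × 13 + 0.2 × 10 = 12.4% at 80%. The passages need to be reconciled; the documents do not settle which figure should give way.

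These results assume two-sided tests, a 60/40 CIS split, equal revascularization in both CIS groups and fixed cell rates.

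**What to change.** In V.A:

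- State the mTICI grades that count as good revascularization.
- Either give the source for 50% on that definition, or tabulate 50%, 80% and 90%.
- For each rate, give power separately for the sizing contrast, the primary fCIS-pCIS test and each secondary test, with the expected good-outcome rates in all treated fCIS and all treated pCIS patients.
- If 50% is kept, say plainly that the primary test has about 65% power with 60 completers.

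In V.B, report the good-v-poor revascularization comparisons within fCIS and within pCIS as estimates with confidence intervals.

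Reconcile the expected pCIS rate across V.A, III.A and VIII.B, so that the safety committee has one stated benchmark for its end-of-Phase-I review under VI.A.

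The cost is a recalculation and some wording. N stays at 60, and no procedure or data item changes, since mTICI is already collected.
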